## Gastroparesis Registry 2 Protocol

**Table 6: Measures of Variability and Minimum Clinically Important Effect Sizes (in  $SD_{\Delta}$  units) detectable with 80% power and 0.05 Type I error for Changes in Continuous Outcome Measures from Baseline to 48 Weeks**

Continuous Outcomes	Mean*	$SD_b$ †	CV†	$\Delta$ †	$SD_{\Delta}$ †	r†	Smaller Subgroup‡§			
							DM	T2DM	Post-Nissen	Not Delayed
							MDE	MDE	MDE	MDE
Symptoms:										
PAGI-SYM: (0-5)										
GCSI	2.9	1.0	0.4	-0.4	1.1	0.44	0.34	0.55	0.37	0.33
Nausea/Vomiting Sub-scale	2.5	1.4	0.6	-0.4	1.4	0.56	0.31	0.50	0.34	0.30
Postprandial Fullness Sub-scale	3.4	1.1	0.3	-0.6	1.3	0.31	0.38	0.62	0.41	0.37
Bloating Sub-scale	3.0	1.6	0.5	-0.2	1.5	0.57	0.30	0.48	0.32	0.29
Upper abdominal sub-score	3.0	1.6	0.5	-0.5	1.5	0.53	0.29	0.48	0.32	0.29
Total hospitalizations in past year	1.9	3.9	2.0	-0.4	3.2	0.66	0.22	0.35	0.24	0.22
Depression/Quality of Life										
BDI score (0-63)	18.8	11.2	0.6	-0.5	9.9	0.61	0.26	0.40	0.28	0.25
State anxiety score (0-80)	44.7	13.6	0.3	0.2	13.9	0.48	0.28	0.46	0.30	0.27
Trait anxiety score (0-80)	44.0	12.5	0.3	0.4	10.8	0.63	0.25	0.40	0.27	0.25
PAGI-QOL total score (0-5)	2.5	1.1	0.4	0.3	0.9	0.64	0.25	0.40	0.26	0.24
SF-36 physical component (0-100)	33.7	10.5	0.3	1.7	9.4	0.60	0.26	0.41	0.28	0.25
SF-36 mental component (0-100)	37.9	12.8	0.3	1.5	12.1	0.56	0.27	0.43	0.29	0.26
Anthropometric:										
BMI kg/m 	27.0	7.3	0.3	0.5	2.6	0.94	0.11	0.18	0.12	0.11
Laboratory measures:										
C-reactive protein (CRP) mg/dL	0.7	1.2	1.7	0.8	0.4	0.95	0.10	0.16	0.11	0.10
ESR (mm/hr)	18.3	19.0	1.0	1.0	15.1	0.69	0.23	0.37	0.25	0.23
HbA1c (%) (for Diabetics only)	7.9	1.9	0.2	0.2	1.9	0.48	n/a	0.46	n/a	n/a
Gastric emptying (scintigraphy):										
% retention at 2 hours	55.4	23.4	0.7	7.0	22.2	0.55	0.27	0.43	0.29	0.26
% retention at 4 hours	25.1	23.4	0.9	6.7	21.2	0.59	0.26	0.42	0.28	0.25

\* Based on data from the GpR Phase I (N=570 participants)

†  $SD_b$  defined as standard deviation (SD) of the mean baseline outcome; CV defined as the coefficient of variation of the baseline outcome data;  $\Delta$  defined as the mean change in outcome from baseline to 48 weeks;  $SD_{\Delta}$  defined as the SD of the change in the outcome measure at 48 weeks; r defined as the intra-class correlation of the measure across time; MDE defined as the minimal detectable effect size (in  $SD_{\Delta}$  units) at 80% power, 0.05 type I error, and r, the correlation between baseline and 48 week measures.

‡ The smaller subgroup is compared to the larger one: DM is all diabetes (N=120) vs idiopathic (N=200), T2DM is Type 2 Diabetes (N=50) vs Type 1 (N=70), Post-Nissen is Post Nissen Fundoplication (N=80) vs others with gastroparesis (N=320); all 6 subgroups must have delayed retention at 4 hour on baseline GES. Not Delayed (N=100) vs Delayed retention (N=400) at 4 hour baseline GES.

§ MDE, expressed in  $SD_{\Delta}$  units, determined from Stata v12 software's "Sample size and power determination for tests of means with repeated measures" (*sampsi\_repmeas*) and the method, ANCOVA, correcting for the mean at baseline. Conversion of the MDE to units of the outcome is computed by multiplying the MDE in Table 6 by  $\Delta$  (mean change of outcome).

As a further aid to sample size justification for analyses related to GpR 2 aims, Figure 1, Panel A shows detectable effect sizes in multiples of SD as a function of the size of the smaller of two subgroups with Type I error = 0.05 and 3 choices for statistical power: 0.50 (inadequate power), 0.80 (good power), and 0.90 (excellent power). Given the subgroup size in the smaller comparison group vs a larger subgroup ( $500 - N_{\text{smaller}}$ ) and outcome measure of interest, Panel A of Figure 1 can be used to find the minimum clinically important detectable effect in SD units; the effect size can be easily converted to the units of the outcome measure of interest using Table 6 (see footnote §).

If the comparison subgroup size is smaller than specified above, then the power will be less than 0.80 for that detectable effect size, or fixing the power at 0.80, the detectable effect size will be larger.

Other studies may require categorical outcomes rather than continuous outcomes. In most cases, a binary event can be defined as the outcome measure in order to judge the adequacy of the sample size, which depends on the Type I error, power, sizes of the subgroups to be compared, and the event rate in the reference subgroup. Table 7 contains information on event rates in reference groups for comparisons of important categorical outcome measures derived from the database from the first phase of the GpR, some of which indicate

improvement over time at 48 weeks (GCSI, PAGI-QOL, SF-36, BDI) and others indicate status at baseline (gastric failure, BMI category, CRP/ESR inflammatory markers, and degree of gastric retention). This mix of important variables is not exhaustive, but the general approach illustrated applies to other categorical outcomes not in Table 7.

**Figure 1. (A) Detectable Effect Size (in SD units) with Power = 0.90, 0.80 and 0.50 and (B) Detectable Relative Risk with Power = 0.80 and Reference Group Effect Rates of 0.5, 0.3 and 0.1 for Analyses Comparing Two Subgroups with Type I error = 0.05 and Total Sample Size of 500**

[figure not shown]

Table 7. Event Rates for Binary Outcome Measures in Reference Subgroups of Interest

Binary Outcomes	Smaller Subgroup*			Not Delayed‡
	Gastroparesis			
	Diabetes	T2DM	Post-Nissen†	
	Rate	Rate	Rate	Rate
Improvement at 48 weeks from baseline:				
Improvement in GCSI (- 0.75 point or less)	0.32	0.29	0.27	0.39
Improvement in PAGA-QOL (0.5 point or more)	0.32	0.30	0.17	0.48
Improvement in SF-36 mental (3.0 points or more)	0.42	0.40	0.33	0.43
Improvement in SF-36 physical (3.0 points or more)	0.42	0.47	0.50	0.41
Improvement in BDI (-5.0 points or less)	0.26	0.24	0.23	0.26
At baseline:				
Gastric failure vs Mild/Compensated	0.44	0.39	0.41	0.22
Not overweight (BMI > 25 kg/m  ) vs Overweight	0.34	0.14	0.71	0.39
Inflammation§ vs not	0.55	0.57	0.35	0.35
Severe 4 hr Gastric Retention vs < 35% retention	0.45	0.32	0.52	n/a

\* The smaller subgroup is compared to the larger one: DM is all diabetes (N=120) vs idiopathic (N=200), T2DM is Type 2 Diabetes (N=50) vs Type 1 (N=70), Post-Nissen is Post Nissen Fundoplication (N=80) vs others with gastroparesis (N=320); all 6 subgroups must have delayed retention at 4 hr on baseline GES. Not Delayed (N=100) vs Delayed retention (N=400) at 4 hour baseline GES.

† Post-Nissen Fundoplication subgroup outcome distributions estimated from the GpR post-surgical group (N=23).

‡ Delayed emptying defined as % gastric retention on scintigraphy at 2 hrs >60% OR gastric retention at 4 hrs > 10%

§ Inflammation defined as CRP > 1.0 mg/dL and /or ESR > 20 mm/hr

¶ Event rates > 0.5: Use 1 – (event rate) to determine power for a given detectable relative risk in Figure 1, Panel B

The event rates in Table 7 can be used in combination with Figure 1, Panel B to find the minimum clinically important relative risk when comparing two subgroups of varying sizes with power = 0.80 and Type I error = 0.05. Detection of relative risks of 2.0 or smaller is possible for event rates near 0.5, even for subgroups as small as 100. Similar sizes of subgroups are needed for event rates near 0.3; if the event rate is as low as 0.1, only relative risks greater than 2.5 will be detectable. Since for this graph, the 2 subgroup sizes must add to 500, then if the combined subgroup size is smaller than 500, the power to detect that relative risk will be less than 0.80.

The calculations presented in Figure 1 assumed two-sided Type I error = 0.05, and a total sample size = 500. The detectable effect size plot in Panel A of Figure 1 assumed power of 0.5, 0.8, and 0.9, and used as the test statistic an ANCOVA with a correlation between baseline and follow-up measures = 0.5 and used Stata (StataCorp 2011. Stata Statistical Software: Release 12. College Station, TX: StataCorp LP) for the calculations. The detectable relative risk plot in Panel B of Figure 1 assumed power = 0.80 and an uncorrected chi-square as the test statistic using the sample size

software of Dupont and Plummer (Dupont W, Plummer WD: Power and Sample Size Calculations: A Review and Computer Program, Controlled Clinical Trials 1990; 11:116-28).

Since the Gastroparesis Registry 2 will generate longitudinal data over time, analytic methods must account for, as applicable, time to events, repeated measurements, counts, or other discrete responses. For time to event data, we will use the Cox proportional hazards regression model with covariates tailored to the hypothesis under investigation. For hypotheses involving repeated measurements, events, counts or other discrete responses, we will use either of two approaches: (1) generalized linear models with generalized estimating equations (GEE) with robust variance estimation to account for the clustering; or, (2) multilevel generalized linear mixed models with random coefficients to account for within patient clustering as well as other sources of variations like clinic effects.

---

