**Table 5. Illustrative GpR 2 Subgroup Comparisons**

Major Subgroup Comparisons	Expected Subgroup Size	
	Smaller	Larger
Delayed Gastric Retention: No vs Yes	100	400
Patients with Delayed Gastric Retention:		
Diabetic vs. Idiopathic	120	200
Diabetes: Type 2 vs Type 1	50	70
Post-Nissen vs Other Gastroparesis	80	320

intra-class correlation coefficient of repeated within-person measures ( $r$ ). GpR 2 analyses of baseline or follow-up data using more variable outcome measures such as total hospitalizations ( $CV=2.0$ ), C-reactive protein ( $CV=1.7$ ), or 2-hr ( $CV=0.7$ ) or 4-hr ( $CV=0.9$ ) gastric emptying times will need larger sample sizes than studies using less variable outcomes such as GSCI ( $CV=0.4$ ), the SF-36 quality of life scales ( $CV=0.3$ ), or HbA1c ( $CV=0.2$ ).

Table 6 also shows, for each potential outcome measure, the minimum clinically important effect size (in SD units) detectable with 80% statistical power and 0.05 two-sided Type I error for four subgroup comparisons with longitudinal outcome measures of change from baseline to 48 weeks, where the smaller subgroup ranges across the sizes shown in Table 5: (1) Diabetes mellitus vs. idiopathic groups, (2) Type 2 vs. Type 1 diabetes, (3) Post Nissen fundoplication vs. other gastroparesis, and (4) Patients with gastroparesis symptoms without vs. with delayed 4 hour gastric emptying by scintigraphy. In every case, across outcomes measures and subgroup sizes, the GpR 2 sample size provides adequate power to detect minimum clinically important effect sizes of  $0.5 SD_{\Delta}$ , or smaller; the smallest effect size is  $0.10 SD_{\Delta}$  and the average effect size in the Table 6 is  $0.30 SD_{\Delta}$ .

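### Table 6 overstates power for change in gastric retention between Not Delayed and Delayed patients, because baseline retention defines the groups and the calculation ignores this

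*Protocol*

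**What the plan says.** Section 7 introduces Table 6 as showing effects "detectable with 80% statistical power and 0.05 two-sided Type I error for four subgroup comparisons", for change from baseline to 48 weeks. One of the four comparisons is "Not Delayed (N=100) vs Delayed retention (N=400) at 4 hour baseline GES" (Table 6, footnote ‡). The footnote to Table 7 gives a wider rule for the same label: "Delayed emptying defined as % gastric retention on scintigraphy at 2 hrs >60% OR gastric retention at 4 hrs > 10"%. Under either version the group comes from the baseline scintigraphy.

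The last two rows of Table 6 are percent retention at 2 and at 4 hours. Their entries in the Not Delayed column are 0.26 and 0.25. Footnote § says that the effects come from a Stata repeated-measures routine "and the method, ANCOVA, correcting for the mean at baseline".

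The last paragraph of section 7 covers analysis of the longitudinal data. For repeated measurements it offers "generalized linear models with generalized estimating equations (GEE) with robust variance estimation to account for the clustering", or multilevel mixed models. It does not say whether baseline is to be a covariate.

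The section also says that the tables are illustrations, and that each proposal must bring its own statistical plan and sample size justification.

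**The concern.** In the 4-hour row the outcome is change in 4-hour retention, and the group is formed largely or wholly by cutting the baseline value of that same measurement. In the 2-hour row the group is formed from the same scan, and under Table 7's rule partly from the 2-hour value itself. Group and baseline covariate must then be correlated. ANCOVA has to separate the group effect from the baseline slope, and the overlap inflates the variance of the group effect. A formula without that inflation gives a detectable effect that is too small.

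The analysis is also delicate. Patients chosen for low baseline retention tend to rise on retest, and those chosen for high retention tend to fall. An analysis that does not adjust properly for baseline will report part of this as a difference in course.

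The figures matter because section 7 offers its tables as an aid to sample size justification, so proposers may carry these cells over. Section 1.4 asks whether the clinical course differs between normal and delayed emptying, and section 3.2.1 has hypotheses about repeat emptying tests.

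**Working it through.** **Inputs from the protocol.** Groups of 100 and 400; two-sided 0.05; 80% power (multiplier 1.960 + 0.842 = 2.80). At 4 hours: mean 25.1, baseline SD 23.4, SD of change 21.2, r = 0.59. At 2 hours: mean 55.4, baseline SD 23.4, r = 0.55.

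**Reproducing the printed cells.** With group uncorrelated with baseline, the ANCOVA detectable effect is 2.80 × √[(1 − r²)(1/100 + 1/400)].

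- 4 hours: 2.80 × √(0.6519 × 0.0125) = 0.253, printed 0.25.
- 2 hours: 2.80 × √(0.6975 × 0.0125) = 0.262, printed 0.26.

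The other three columns of both rows reproduce in the same way. The change-score formula gives 0.284 and 0.297, and ANCOVA rescaled to SD of change gives 0.279 and 0.276. Neither matches, so these are ANCOVA figures in units of the outcome's SD. At the rounded printed values the formula gives power of 79.1% (4 hours) and 79.5% (2 hours).

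**Allowing for the overlap.** With 20% of patients in the Not Delayed group, the correlation of group with baseline is ρ = (difference in group baseline means) × √(0.2 × 0.8) / SD. The variance is multiplied by 1/(1 − ρ²), and the detectable effect by the square root of that. The Delayed mean follows from the overall mean: (overall − 0.2 × Not Delayed mean) / 0.8.

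The Not Delayed means are assumptions. At 4 hours the range is 0% to 10%, because a patient who is not delayed has 4-hour retention of 10% or less. At 2 hours the range is 25% to 45%.

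| Row | Assumed Not Delayed mean | Difference | ρ | 1/(1 − ρ²) | Detectable effect | Power at printed value |
|---|---|---|---|---|---|---|
| 4 h | 0 | 31.4 | 0.54 | 1.40 | 0.30 | 65% |
| 4 h | 5 | 25.1 | 0.43 | 1.23 | 0.28 | 71% |
| 4 h | 10 | 18.9 | 0.32 | 1.12 | 0.27 | 75% |
| 2 h | 25 | 38.0 | 0.65 | 1.73 | 0.34 | 56% |
| 2 h | 35 | 25.5 | 0.44 | 1.23 | 0.29 | 71% |
| 2 h | 45 | 13.0 | 0.22 | 1.05 | 0.27 | 78% |

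**Regression to the mean, with no true group difference.** Equal SDs at both times are consistent with Table 6: 1 − 21.2²/(2 × 23.4²) = 0.59. The expected spurious difference in change is then (1 − 0.59) × difference in baseline means. Over the 4-hour range this is 0.41 × 18.9 = 7.7 to 0.41 × 31.4 = 12.9 points. The printed 0.25 corresponds to 0.25 × 23.4 = 5.9 points.

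**Simulation under the null (500 patients, 4-hour figures).**

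- Follow-up linear in baseline, whether baseline is normal or skewed: baseline-adjusted ANCOVA rejects about 5% of the time, with bias near zero. An unadjusted change-score test rejects 99% to 100% of the time.
- Baseline and follow-up both log-normal with the same mean and SD, cut at 10% retention, so that the relation is curved: linear ANCOVA rejects close to 60% of the time, with a bias of nearly 5 points. The change-score test rejects about 98% of the time.

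The log-normal shape is an assumption. The protocol gives no joint distribution.

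**The case against.** The strongest reply is that the stated method is ANCOVA on baseline, which is the right protection. A reader might infer from the table's reference to changes, or from the GEE and mixed-model paragraph, that regression to the mean will be counted as a group difference and that a significant result is almost guaranteed. The documents do not support that. The 98% to 100% rejection rates belong to an unadjusted change-score test, which the protocol nowhere specifies. The closing paragraph of section 7 lists model families, names no contrast for retention, and does not rule out baseline adjustment. What remains is that it does not require adjustment either, and that linear adjustment suffices only if the relation is close to linear. Skewness alone does no harm; curvature does.

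A reader might also put the true power near 50%. That needs a normal baseline cut at its lowest 20% (ρ = 0.70, detectable effect 0.35). With mean 25.1 and SD 23.4, such a distribution puts about 14% of patients below zero retention, so it is not credible at 4 hours.

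Nor does the n/a in Table 7 for "Severe 4 hr Gastric Retention vs < 35% retention" set a precedent. That row describes baseline status, and severe retention cannot occur in patients who are not delayed. Change at 48 weeks can vary in both groups.

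Finally, the table is illustrative and each proposal needs its own calculation. This is correct and limits the consequences, but the two printed figures are still wrong for the comparison they label.

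**Conclusion.** The point stands in a limited form. The two Not Delayed retention cells rest on an independence assumption that the group definition rules out, so their detectable effects are too small and 80% power is not delivered. Under the stated assumptions the 4-hour effect is about 0.27 to 0.30 rather than 0.25, with power at 0.25 of about 65% to 75%. The 2-hour effect is about 0.27 to 0.34 rather than 0.26, with power at 0.26 of about 56% to 78%. The direction is certain. The size depends on group means that the protocol does not give but the first registry should hold.

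Regression to the mean is a risk that the text leaves open, not an error that it commits. It would arise with unadjusted change scores or a group-by-time contrast without baseline adjustment, and to a lesser degree with linear ANCOVA if the relation is curved. The comparison need not be banned. No overall sample size is affected, and the corrected effects remain below the 0.5 SD that section 7 describes as adequately powered.

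**What to change.** In Table 6, recompute the Not Delayed entries of the two retention rows. Multiply the variance by 1/(1 − ρ²), with ρ taken from first-registry data under the definition of delayed emptying that will be used. Alternatively, mark the two cells n/a.

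Add one sentence to section 7: any comparison of change in retention between groups defined by baseline retention must condition on continuous baseline retention at both 2 and 4 hours, include a check for non-linearity such as a spline, and not rest on unadjusted change scores. Both time points are needed because the 2-hour or 4-hour rule makes the group depend on both.

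The cost is two illustrative figures that become slightly less favourable and one added sentence. No new patients or data are needed.

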## Gastroparesis Registry 2 Protocol

### 8. Human participants issues

---

#### 8.1. Overview and IRB approval

The Gastroparesis Registry 2 study is not a treatment study. Patients will continue to receive care for their clinical condition. The study protocol, consent forms, and data collection forms will be submitted to each clinical center's IRB and to the SDRC's IRB. Additionally, each clinical center will submit to their IRB any recruitment materials to be used at their site. A site may not initiate any patient contact about the Gastroparesis Registry 2 until the site has IRB approval and the SDRC has certified the site for initiation of patient activities. Consent forms must have IRB approval. Sites must provide the SDRC with copies of the initial IRB approval notice and subsequent renewals, as well as copies of the IRB approved consent statements. All study personnel will have completed training in the Protection of Human Subjects per NIH guidelines.

The proposed study anticipates recruiting a significant proportion of racial/ethnic minorities (Black or African American, Hispanics or Latino, Asian, American Indian/Alaska Native, Native Hawaiian or other Pacific Islander) as well as non-Hispanic white subjects. We anticipate that the patients recruited from diverse sources, including community and tertiary referral populations, will capture the entire spectrum of gastroparesis.

All participants enrolled in the GpR 2 will receive a standard of care for gastroparesis and identified associated medical problems as defined by the GpCRC Steering Committee (see SOP IV: Standard of Care for Patients with Gastroparesis). This will include provision of health care counseling and educational materials at enrollment and on an ongoing basis during follow-up.

#### 8.2. Informed consent

Template consents will be prepared for the study. Sites may reformat and reword information to conform to their local requirements. A signed consent form will be obtained from the subject. The consent form will describe the purpose of the study, the procedures to be followed, and the risks and benefits of participation. A copy of the consent form will be given to the participant and this fact will be documented in the participant's record.

#### 8.3. Participant confidentiality

All laboratory specimens, evaluation forms, reports, and other records that are part of the study data collection and entry materials will be identified by coded number only to maintain participant confidentiality. All records will be kept in locked file cabinets with access limited to the GpR 2 investigators. All computer entry and networking programs will identify patients by patient identification number. Clinical information will not be released without written permission of the subject, except as necessary for monitoring by the IRB or DSMB. Clinical information may be reviewed during site visits, but use of personal identifiers will be avoided. Consent procedures and forms, and the communication, transmission and storage of patient data will comply with individual site IRB and NIH requirements for compliance with The Health Insurance Portability and Accountability Act (HIPAA).

#### 8.4. Concerns related to specimen banking

It is anticipated that serum, plasma, and DNA from the participants will be stored for future studies related to gastroparesis and possibly other diseases. These samples will be stored in NIDDK central repositories. The GpCRC Steering Committee will develop specific guidelines addressing the issues such as (a) obtaining a separate informed consent, (b) storage, (c) transportation of the material, (d) who will have access to the material, and (e) what investigations are to be conducted.

**8.5. Participant withdrawal**

If a participant chooses to withdraw from the GpR 2, all data collected up to the point of withdrawal will remain in the GpR 2, but no further data may be collected. This is consistent with HIPAA guidelines and regulations.

---

## 9. Safety monitoring

---

GpR 2 is an observational multicenter study and each participating clinical center will follow local IRB guidelines to monitor and report unanticipated or adverse events to ensure participant safety. Since the adverse event definitions and reporting requirements for unanticipated events may differ at each participating site, the GpR 2 definitions and procedures for adverse event reporting are designed to satisfy a wide spectrum of interpretations of the Common Rule requirements.

